6.2.4 Alternate Analysis Methods

A negative binomial response is assumed (the overdispersion parameter $k > 0$). If this assumption does not hold, then a Poisson response may be adequate. If the negative binomial model does not fit adequately, as mentioned in Section 6.2.3, then k will be set to 0 and a Poisson model will be fit to the data.

6.2.5 Sensitivity Analysis

Morrow County, OH withdrew from the study post randomization but prior to the study initiation in January 2020. In response to this one and possibly more communities withdrawing from the HCS study and thereby yielding lower power for the subsequent PP analysis, additional power simulations were conducted to account for withdrawal scenarios. This section reports the findings from the additional simulations.

Table 3 below shows power estimates that were generated by considering the following:

- Morrow County, OH only withdraws from the HCS;

HCS Protocol (MP0048)

Statistical Analysis Plan for the HCS Main Trial Results

- Morrow County and one to four additional communities per RS per intervention arm combination withdraws from the HCS (from 8 to 32 additional communities).

These power calculations were conducted as described in Section 3.3 for the primary analysis power estimation. Based on these simulations, the withdrawal of Morrow County, OH does not affect the power of the study in a substantial manner, nor does the withdrawal of one or two additional communities.

Table 3. Power calculations for underlying reduction in the rate of opioid OD deaths during the evaluation period between Wave 1 and 2 communities, assuming numerous community drop-out scenarios. Empirical standard error estimates were utilized. Treatment allocation was not included in the initial model to extract parameter estimates, only covariates (RS and rural/urban status). A new treatment allocation was determined within each replication, balanced within RS (KY, MA, NY, OH; except for OH which has 19 communities).

Intervention Effect ¹	Relative Rate Of Opioid OD Deaths	Morrow ONLY ²	1	2	3	4
40%	0.60	>0.999	>0.999	0.999	0.999	0.997
30%	0.70	0.995	0.993	0.992	0.982	0.968
25%	0.75	0.957	0.956	0.950	0.916	0.891
23%	0.77	0.927	0.916	0.907	0.869	0.835
22%	0.78	0.898	0.888	0.877	0.833	0.802
21%	0.79	0.869	0.863	0.846	0.801	0.770
20%	0.80	0.835	0.818	0.812	0.759	0.736

¹ Percent reduction in rate for Wave 1 versus Wave 2 communities.

² Scenarios in which only Morrow County, OH withdrew, with the addition of the potential withdrawal of 1, 2, 3 or 4 additional communities.

With this in mind, the primary analysis described in Section 6.2.1.1 will be replicated using a PP framework. In this case, the degrees of freedom that will be used for all hypothesis tests will be changed from 60 to 59 to account for Morrow County's withdrawal.

The following sensitivity analyses were also conducted after Version 3.0 of the SAP was implemented and results disseminated.

1. To assess the impact of using negative binomial or Poisson regression to model the rate of opioid overdose deaths during the evaluation period, we will compare the following:
 - a. The effect of the CTH intervention on the rate of opioid overdose deaths during the evaluation period under a GEE-type negative binomial regression model.
 - b. The effect of the CTH intervention on the rate of opioid overdose deaths during the evaluation period under a GEE-type Poisson regression model.
2. To assess the impact of using various functional forms of the baseline rate of opioid overdose deaths as a covariate, we will compare the following:
 - a. The effect of the CTH intervention on the rate of opioid overdose deaths during the evaluation period under a model that uses the baseline rate of opioid overdose deaths as a covariate.

- b. The effect of the CTH intervention on the rate of opioid overdose deaths during the evaluation period under a model that uses the log of the baseline rate of opioid overdose deaths as a covariate.
3. To assess the impact of assuming that the effect of urban/rural status on the rate of opioid overdose deaths during the evaluation period is the same across research sites, we will compare the following:
 - a. The effect of the CTH intervention on the rate of opioid overdose deaths during the evaluation period under a model that does not include an interaction between urban/rural status and research site.
 - b. The effect of the CTH intervention on the rate of opioid overdose deaths during the evaluation period under a model that includes an interaction between urban/rural status and research site.
4. To assess the impact of assuming that the effect of the CTH intervention on the rate of opioid overdose deaths during the evaluation period is the same across research sites, we will compare the following:
 - a. The effect of the CTH intervention on the rate of opioid overdose deaths during the evaluation period under a model that does not include an interaction between wave and research site.
 - b. The effect of the CTH intervention on the rate of opioid overdose deaths during the evaluation period under a model that includes an interaction between wave and research site. In this case, the effect of the CTH intervention on the rate of opioid overdose deaths during the evaluation period is an average of the site-specific estimates of the CTH intervention on the rate of opioid overdose deaths.

To assess the impact of 2 or more of these assumptions on the effect of the CTH intervention on the rate of opioid overdose deaths during the evaluation period, we will also combine sensitivity analyses across these 4 types, resulting in a total of 16 sensitivity analyses.

6.2.6 Subgroup Analysis

There are 5 planned subgroup analyses using the following stratification variables:

- RS (KY, MA, NY, OH)
- Rural/urban status
- Sex (female, male, missing)
- Race/ethnicity (Black, Hispanic, White, Other)
- Age (18-34 years, 35-54 years, 55+ years)

For each subgroup, a separate model will be fit using the ITT framework. Each model will be similar to the model used for the primary analysis described in Section 6.2.1.1 but will also include fixed effects for the stratification variable as well as an interaction between wave and the stratification variable. When the stratification variable is sex, race/ethnicity, or age, RS and rural/urban status will also be included in the model as fixed effects. The subgroup analysis using sex, race/ethnicity, and age will need to account for repeated measures across the levels of the stratification variable within a community and so a Generalized Estimating Equation (GEE)-type negative binomial (or Poisson) regression model will be used.

Note that subgroup analyses for the community level variables, RS and rural/urban status, will use the same data structure as that used for the primary analysis. The subgroup analysis using sex, race/ethnicity, and age requires the data structure to be modified such that there is a separate record for each stratification variable level within a community. While design variables such as RS, rural/urban status, and baseline rate of opioid OD deaths will not change for each of these records, the dependent variable, offset, and baseline rate of the outcome of interest will need to be modified so that they are specific to each stratification variable level.

To account for multiple comparisons arising from subgroup analyses performed within this analysis, the FDR will be controlled for all effect modification interaction tests between wave and the stratification variable as well as pairwise tests between levels of a stratification variables using Benjamini-Hochberg (1995)¹⁴ FDR-adjusted p-values using the following process:

- Step 1: All p-values from all interaction tests will be gathered together and the Benjamini-Hochberg (1995)¹⁴ procedure will be applied to obtain FDR-adjusted p-values.
- Step 2: Amongst all interaction tests where the FDR-adjusted p-value is statistically significant at a 0.05 level, all p-values from all corresponding pairwise tests will be gathered together and the Benjamini-Hochberg (1995)¹⁴ procedure will be applied to obtain FDR-adjusted p-values.

For each test of effect modification, adjusted rates within Wave 1 and 2 and the adjusted relative rate between Wave 1 and 2 within each level of a stratification variable (as well as 95% simultaneous CI using a Bonferroni correction that were added after Version 3.0 of the SAP was implemented and results disseminated) will be reported, in addition to the FDR-adjusted p-value associated with the interaction test.

- If the test for effect modification is not statistically significant at the 0.05 level, no further reporting will be performed.
- If the test for effect modification is statistically significant at the 0.05 level, the following will be reported:
 - estimate of the ratio of the relative rate between Wave 1 and 2 (as well as 95% simultaneous CI using a Bonferroni correction) between any 2 subgroups; and
 - pairwise FDR-adjusted p-value between any 2 subgroups.

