8.3 Appendix 3: SAS Code Examples

Exhibit 8.3.1: An example of SAS PROC GLIMMIX code to be used for the primary analysis of the primary hypothesis.

```
PROC GLIMMIX DATA=ALLCOMM empirical = FIRORES (or ROOT) MAXLMMUPDATE=100 ;  
TITLE1 "NEGATIVE BINOMIAL MODEL BASED ON GLIMMIX";  
MODEL NOPDEATHS = OPDEATH_BL SITE2 SITE3 SITE4 RURAL GRP_CODE /  
OFFSET=LOGCOMM_POP ddfm = none ddf = 60, 60, 60, 60, 60, 60, 60, 60 DIST=NEGBIN S;
```

where:

NOPDEATHS = primary outcome, the number of opioid OD deaths during the evaluation period for each community

OPDEATH_BL = baseline rate of opioid OD deaths for each community

SITE2, SITE3, SITE4 = indicator variables for RS, referencing comparison to SITE = 1 (insert RS that = 1)

RURAL = rural/urban status for each community (1 = rural, 0 = urban)

GRP_CODE = intervention arm (1 = CTH intervention, 0 = wait-list control)

LOGCOMM_POP = natural log of community population size during the evaluation period, which is implicitly in the equation accounting for variation in population size, and hence the variation in denominators for rates among communities

DIST = NEGBIN signifies a negative binomial error structure; essentially allowing the underlying Poisson rate of opioid OD deaths during the evaluation period to vary across communities

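### SAP 6.2.6: if the rural/urban interaction passes step 1, step 2 repeats the same test in a different family, so one hypothesis is reported with two FDR-adjusted p-values

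*SAP*

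**What the plan says.** SAP 6.2.6 states: "There are 5 planned subgroup analyses using the following stratification variables". They are research site, rural/urban status, sex, race/ethnicity and age. Each gets its own model with a wave-by-variable interaction.

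Multiplicity is handled in two steps:

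- **Step 1.** "All p-values from all interaction tests will be gathered together", and Benjamini-Hochberg is applied to them.
- **Step 2.** Among the variables whose step 1 adjusted p-value is significant at 0.05, "all p-values from all corresponding pairwise tests will be gathered together", and Benjamini-Hochberg is applied to that pool.

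The adjusted interaction p-value is reported for every variable. If it is not significant, reporting stops there. If it is, the SAP adds the ratio of the Wave 1/Wave 2 relative rates between levels, with a confidence interval, and the "pairwise FDR-adjusted p-value between any 2 subgroups".

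Appendix 3 of the SAP codes rural/urban as a single indicator: "RURAL = rural/urban status for each community (1 = rural, 0 = urban". Section 6.2.6 makes no exception for a two-level variable and does not say which adjusted p-value governs if the two differ.

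**The concern.** With three or more levels, the interaction test and the pairwise tests ask different questions, so a second step makes sense. With two levels there is one pair, and comparing that pair is the interaction test. Step 2 then adjusts an already adjusted hypothesis again, over a family whose size depends on which other variables happened to pass.

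Three things follow if rural/urban passes step 1:

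- The results carry two different p-values for one hypothesis, both labelled FDR-adjusted, and an author could quote either.
- In some configurations the second value is above 0.05 after the first was below it.
- A hypothesis already settled in step 1 takes a place in the step 2 pool and alters the adjusted p-values of the other variables' pairs.

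Rural/urban is one of only two subgroup analyses planned in Protocol 9.4.5, so a positive result would probably be quoted. The Protocol's own follow-up, tests of trial arm within each level, would not repeat the interaction test. The duplication comes from the SAP's pairwise follow-up.

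**Working it through.** **Inputs.** Levels are taken from SAP 6.2.6 and, for rural/urban, Appendix 3. A variable with L levels has L(L−1)/2 pairs.

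| Variable | Levels | Pairs |
|---|---|---|
| Research site | 4 | 6 |
| Rural/urban | 2 | 1 |
| Sex (with a missing level) | 3 | 3 |
| Race/ethnicity | 4 | 6 |
| Age | 3 | 3 |

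The five variables reproduce the SAP's count of five analyses, so the step 1 family has m = 5. The step 2 family, when rural/urban passes, has between 1 and 6+1+3+6+3 = 19 tests.

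**Same test.** Write the rural/urban model with a wave effect b and a wave-by-rural interaction d. The log relative rate is b in urban and b + d in rural communities. Their difference is d, so the pairwise ratio of relative rates is exp(d). With the same standard error and degrees of freedom, the p-values coincide. As a numerical check, a negative binomial model with robust standard errors was fitted to simulated counts. It used the wave, site and rural/urban layout of the 67 communities in SAP Appendix 1 and k = 0.0431. The interaction p-value and the rural-minus-urban contrast p-value were both 0.00349181.

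**Adjustment.** For p-values ordered p(1) ≤ … ≤ p(m), the adjusted value at rank i is the smallest of m·p(j)/j over j ≥ i, capped at 1.

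**Case A: rural/urban alone passes.** Interaction p-values, illustrative: 0.009 (rural/urban), 0.2, 0.4, 0.6, 0.7.

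- Step 1: 5 × 0.009 / 1 = 0.045.
- Step 2: a family of one, so 1 × 0.009 / 1 = 0.009, the raw value.
- Ratio: 0.045 / 0.009 = 5.

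Five is the ceiling, because step 1 is at most 5 × raw and step 2 is at least raw. Both values are below 0.05.

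**Case B: site also passes.** Interaction p-values, illustrative: 0.002 (site), 0.018 (rural/urban), 0.4, 0.6, 0.7. Six site pairs: 0.0008, 0.03, 0.04, 0.2, 0.5, 0.7.

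- Step 1: site 5 × 0.002 / 1 = 0.010; rural/urban 5 × 0.018 / 2 = 0.045. Both pass.
- Step 2, m = 7: rural/urban is at rank 2, 7 × 0.018 / 2 = 0.063. The next two ranks give 7 × 0.03 / 3 = 0.070 and 7 × 0.04 / 4 = 0.070, so 0.063 stands.

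The split also arises when the site p-values come from one coherent set of estimates. Site log relative rates of −2.4, 0, 0 and 2.4 in standard-error units give an omnibus p of 0.0092 and pairs of 0.0007, 0.0897 (four times) and 1.0. With rural/urban at 0.018 and the rest null, step 1 is again 0.045 and step 2 is 7 × 0.018 / 2 = 0.063.

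**Effect on the other pairs, Case B.** Without the repeated test, m = 6. The site pairs at raw 0.03 and 0.04 give 6 × 0.03 / 2 = 0.090 and 6 × 0.04 / 3 = 0.080, so both become 0.080 instead of 0.070. The smallest goes from 7 × 0.0008 = 0.0056 to 6 × 0.0008 = 0.0048.

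**Frequency, under assumed effects only.** In one simulation of 20,000 sets with mixed effect sizes, rural/urban passed step 1 in 4,245, and step 2 was 0.05 or more in 152 of these (152 / 4,245 = 3.6%). In another, with the rural/urban interaction alone real at 80% raw power, it passed in 60%; it was the only one to pass in 91% of those, and the two values fell on opposite sides of 0.05 in 0.1%. With site and race/ethnicity also real, that last figure was 3.4%. With no true interaction, rural/urban passed in about 1.1% of sets, and opposite sides occurred in about 0.015%.

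**The case against.** The case for leaving the text alone is that this is a conditional redundancy that seldom affects a decision. Much of that stands, and it rules out several stronger readings that a reader might infer.

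- **That rural/urban always gets two p-values.** It does not. SAP 6.2.6 stops reporting if the interaction fails step 1.
- **That the fivefold gap flips a conclusion.** It does not. That gap belongs to the case where rural/urban alone passes, and both values are then below 0.05. Opposite sides needs a second variable to pass.
- **That the step 2 value in Case A has no multiplicity protection, or that false findings are inflated.** The documents do not support this. The pairwise value is reached only after Benjamini-Hochberg rejection over five tests, and requiring both steps is never more lenient than step 1 alone. The fault is that a raw p-value carries an FDR-adjusted label.
- **That the conflict is common.** It is one-way (step 1 significant, step 2 not), and its frequency rests on assumed interaction effects. SAP Table 1 gives power for the overall effect only.
- **That rural/urban was a randomization stratum.** SAP 3.2 stratifies by research site and uses rural/urban as a balance constraint.

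It can also be said that 6.2.6 does not spell out the standard error or degrees of freedom for these tests, so identity is an assumption. That is fair. However, each model is described as similar to the primary one and no second method is named. Finally, if step 2 were run separately for each variable, the conflict would vanish, but step 2 would then always print the raw value for rural/urban. The text reads as one pool.

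**Conclusion.** The point holds as a small reporting defect. Followed literally, SAP 6.2.6 prints two different FDR-adjusted p-values for the rural/urban interaction whenever it passes step 1 and the two families give different results. Step 2 is five times smaller than step 1 when rural/urban alone passes. It can be above 0.05 (0.063 against 0.045) when another variable passes too. The repeated test also moves other pairs' adjusted values, by about 0.01 in the example.

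This rests on the same standard error and degrees of freedom being used for both tests, and on step 2 being pooled across variables. The illustrative p-values are chosen, not observed; that both outcomes can occur does not depend on them, but how often they occur does. The same issue would affect sex if its missing level turned out empty. The primary analysis is untouched.

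**What to change.** Add to step 2 of SAP 6.2.6, in substance:

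> For a variable with two analysed levels, the pairwise comparison is the interaction test. Only its step 1 FDR-adjusted p-value is reported, with the ratio of relative rates and its confidence interval, and it does not enter step 2. Step 2 pools pairwise tests only for variables with three or more levels.

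This leaves a single value, 0.045, in both examples, and also covers sex if no deaths fall in the missing category.

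The cost is one sentence and no new model. The printed p-value for the two-level contrast will usually be larger (0.045 rather than 0.009 in Case A), although in Case B the value removed is the stricter 0.063. Other step 2 values can shift, as with 0.070 to 0.080 above. SAP 6.2.6 itself records that results were disseminated after Version 3.0, so the change should be labelled post hoc. The documents do not show whether a two-level variable passed step 1. If none did, no reported figure changes.

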6.3 Missing Data

The analyses for the primary hypothesis will be done using an ITT framework defined as the inclusion of all communities randomized into the HCS, analyzed according to intervention arm. There will be no missing data for the primary outcome of HCS main trial as all data will be obtained from administrative data sources. Multiple imputation or other missing data methods will not be performed to account for suppressed data at the subgroup level within a community (e.g., sex, race/ethnicity, age). In this case, subgroups with suppressed data will be excluded from the analysis and the amount of suppressed data will be summarized.

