1.3 SAP Revision History

Ver.	Justification for change	Date	Approved
1.0	SAP approved by the HCS StaDA-WG on May 5, 2021 and by the HCS Steering Committee on May 21, 2021.	2021-05-21	NAV*
1.1	At the behest of the Steering Committee reducing the scope of MP0048 to opioid overdose deaths.	2022-09-08	NAV*
1.2	Modified Section 6.2.4 to clarify when a Poisson or Negative Binomial model would be used. Modified the section 6.2.6 to include investigations into interactions between intervention and Age, Race/Ethnicity, and Sex. Modified Section 6.7 to define additional tables to cover additional subgroup analyses.	2022-10-19	NAV*
1.3	Modified Sections 6.2.6 and 6.7 to reflect decisions made by DCC StatOps and StaDA-WG regarding FDR and potential displays.	2023-05-12	NAV*
2.0	Finalized language in section 6.5 on the reporting of AE/SAE. Created pdf of SAP.	2023-06-05	NAV*
3.0	Added language to section 6.2.6 to indicate that individual point estimates will be provided for all subgroups for descriptive purposes at the urging of the HCS SC who made this request at their meeting 2023-06-30.	2023-07-06	NAV*
4.0	Added language to section 6.2.5 to indicate post-hoc sensitivity analyses that were conducted.	2023-08-11	DCB*

	Revised language in section 6.2.6 to describe reporting of individual point estimates and confidence intervals for all subgroups. Added language to section 6.4 to indicate post-hoc analyses that were conducted.		
5.0	Added NCT number to first page. Added language to section 6.4 to indicate post-hoc estimation methods for “deaths averted” calculation.	2023-11-16	NAV*

*Note: NAV = [name], Director of DCC StatOps; DCB = [name], Senior Research Statistician, DCC StatOps

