In our simulation study, we assumed that the population parameters just described were reflective of the true parameters for the Wave 2 communities during the evaluation period. The analyses were conducted as described in Section 6.2.1.1, with the exception that the baseline rate of opioid OD deaths was not incorporated into the model as a covariate, thus providing conservative power estimates.

Table 1 provides power estimates for a variety of differences in the rate of opioid OD deaths during the evaluation period between the Wave 1 and Wave 2 communities. As can be seen, we have greater than 99% power to detect a 40% (i.e., relative rate 0.60) reduction and at least 83% power for any reduction of 20% or more.

Table 1. Power calculation for underlying reduction in the rate of opioid OD deaths during the evaluation period between intervention and wait-list control arms. Empirical SE estimates were utilized. Treatment allocation was not included in the initial model to extract parameter estimates, only covariates (RS and rural/urban status). A new treatment allocation was determined within each replication, balanced within RS (KY, MA, NY, OH; except for OH which has 19 communities).

Intervention Effect	Relative Rate of Opioid OD Deaths	Power
40%	0.60	0.999
25%	0.75	0.961
24%	0.76	0.943
23%	0.77	0.925
22%	0.78	0.899
21%	0.79	0.866
20%	0.80	0.832
19%	0.81	0.792

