8.2 Appendix 2: Additional RS-specific inclusion criteria for communities enrolled in the HCS

Criteria	Kentucky	Massachusetts	New York	Ohio
Number of communities	16 counties	16 cities/towns	16 counties	19 counties
Additional criteria	Selected counties that had (1) a syringe service program (marker of community readiness), (2) a jail, (3) ≥ 1 buprenorphine-waivered provider, and (4) ≥ 5 opioid overdose deaths in 2017	Selected to minimize proximity and contamination, favored communities with an anchor office-based addiction treatment program and a pre-existing substance use coalition	Selected the communities of Buffalo in Erie County, Rochester in Monroe County, and the Brookhaven township in Suffolk County to keep size comparable	Randomly selected counties stratified by urban/rural that (1) were not contiguous and (2) did not share an alcohol, drug and mental health board

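### SAP 6.3 deletes suppressed community-by-level death records from the sex, race/ethnicity and age models although the protocol describes small counts being available for analysis; if low death counts trigger suppression, the deletion selects on the outcome

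*SAP*

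**What the plan says.** SAP 1.3 records that version 1.1 narrowed this plan by "reducing the scope of MP0048 to opioid overdose deaths", so the suppression rule concerns death counts only.

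SAP 6.2.6 restructures the data for the sex, race/ethnicity and age models so that each level within a community has its own record. It says that "the dependent variable, offset, and baseline rate of the outcome of interest will need to be modified so that they are specific" to each level. Whatever the interaction test shows, it reports "adjusted rates within Wave 1 and 2 and the adjusted relative rate between Wave 1 and 2 within each level of a stratification variable".

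SAP 6.3 then gives the rule: "Multiple imputation or other missing data methods will not be performed to account for suppressed data at the subgroup level within a community", and "subgroups with suppressed data will be excluded from the analysis and the amount of suppressed data will be summarized". For community totals it says: "There will be no missing data for the primary outcome of HCS main trial as all data will be obtained from administrative data sources".

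The protocol describes data access in the state plans of section 10.1.8.1. Kentucky, New York and Ohio each state that counts normally suppressed are released for analysis but never made public. Massachusetts staff have individual-level access to death information. The Massachusetts suppression range of 1 to 10 individuals is stated for the other state data sources.

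Protocol 9.4.6 calls the sex and race analyses exploratory and says that small community counts may require levels to be grouped or redefined.

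**The concern.** The unit that SAP 6.3 removes is a community-by-level record. The section does not say which field triggers suppression (deaths, population offset or baseline rate), at which site, at what threshold, or whether zeros count. The protocol's state plans link suppression to small counts, so a low death count is a natural candidate. If that is the trigger, a record stays in or drops out according to its own outcome, and each level of a variable is estimated on a different set of communities. The level-specific rates and relative rates would then not be comparable with each other.

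The rule also sits awkwardly with the protocol. Where small counts are released for analysis, there is nothing to exclude. At stake are the level-specific results for sex, race/ethnicity and age, most of all in sparse race/ethnicity levels.

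**Working it through.** **1. Are small counts available to the analysts?** Protocol 10.1.8.1 says so for Kentucky and Ohio (sent to the Data Coordinating Center, DCC) and for New York (released for analysis). For Massachusetts it gives individual-level death access in the state health department's environment, but no explicit release of small demographic cells to the DCC. The SAP cites protocol 1.20; the logged changes in 1.21 and 1.22 concern the study end date and personnel entries. Small totals must also reach the primary model, because SAP 6.3 expects no missing primary data while Kentucky counties could qualify (SAP Appendix 2) with as few as "5 opioid overdose deaths in 2017". That last point concerns totals, not demographic cells.

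**2. Simulation inputs.** From the documents: 67 communities with wave, site and rural status (SAP Appendix 1), k = 0.0431 (SAP 3.3), and the 1 to 10 range (protocol 10.1.8.1, printed for non-death data, so its use for deaths is an assumption). Assumed:
- level shares: age 30/45/25%, sex 30/70%, race/ethnicity 10/8/77/5%; log SD of shares 0.3 or 0.8
- correlation of 0.5 between baseline and evaluation community effects
- sex level 'missing' omitted
- Massachusetts either at the overall mean or at the 2016 eligibility minimum, 150/16 = 9.4 deaths per community

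**3. Calibration to the plan's figure.** SAP 3.3 states "at least 83% power for any reduction of 20% or more" (0.832 at relative rate 0.80). Community sizes are not printed, so this can be matched but not independently reproduced. Lognormal sizes with log SD 0.7, 1.0 or 1.3 and mean deaths of 24, 31 or 42 give power of 0.832, 0.830 and 0.822. Null rejection is 0.06 to 0.08, against 0.075 in protocol Table 12.

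**4. Model.** For community i and level l, Y is negative binomial with variance μ + kμ² and

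log μ = log(population) + site + rural + baseline rate + level + wave + wave × level,

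with level-specific population and baseline rate. SAP 6.2.6 is itself unclear on the baseline rate: it says that rate is unchanged across records and also that it becomes level-specific. The second reading was used. The true relative rate is 0.80 in every level, with 500 replicates in each of 12 settings.

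**5. Results.**

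| Masking | Records lost | Relative rates | Adjusted rate ÷ full-data rate |
|---|---|---|---|
| None (all counts released) | 0 | unchanged | 1 |
| Massachusetts, 1–10 | 9–19% | 0.77–0.81 | 0.87–1.03 (sparse race levels 0.87–0.99) |
| Massachusetts, 0–10 | 15–23% | 0.77–0.82 | 1.01–1.10 |
| Massachusetts, 1–10 in either period | 13–22% | 0.77–0.82 | not tabulated |

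Check of the second row: 39 to 78% of Massachusetts records are lost, and 16/67 × 39% = 9% and 16/67 × 78% = 19%.

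Interaction tests in the second row reject in 2 to 10% of runs, against 3 to 10% without deletion. These omit the false discovery rate step in SAP 6.2.6, so they are not the plan's error rates. With Massachusetts at the minimum, 14 to 34% of age models could not be estimated. In a 300-run check of one such setting, every failure had only zero cells left in Massachusetts.

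**6. Why the direction depends on zeros.** At 9.4 deaths per community, a level with an 8% share expects 9.4 × 0.08 = 0.75 deaths. Ignoring overdispersion, P(0) = exp(−0.75) = 0.47, and 11 or more is practically impossible. With 1–10 masked and zeros kept, about half of these records survive and all are zeros, so the rate falls. With zeros masked too, only cells of 11 or more survive anywhere in Massachusetts, so rates rise.

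**7. All-site masking, illustrative only.** With 1–10 masked everywhere, 48 to 75% of records go and the race model is not estimable in 44 to 100% of runs. This contradicts protocol 10.1.8.1 and carries no weight in the conclusion.

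**The case against.** The strongest reply is that the harm rests on a premise the documents never establish. No passage shows a masked death cell. If counts flow as protocol 10.1.8.1 describes, the exclusion sentence is an unused contingency. Massachusetts has no explicit release statement, so a fallback rule for its cells is compatible with the protocol. Triggers and thresholds may be defined in the technical specifications or data use agreements, which are not available here. In the only plausible masking case the relative rates barely move, and the protocol treats the sex and race analyses as exploratory. All of this stands, and it limits the size of the point.

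It does not rescue the rule. The sentence is an operative instruction that bars every alternative. If no cell is masked, replacing it costs nothing. If some are masked because deaths are few, following it exactly lets the outcome decide which records enter estimates that are always reported.

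A reader might infer that the disseminated subgroup results are biased, or that the race/ethnicity models collapse. The documents support neither: the first needs evidence of masking, and the second needs masking at all sites. A reader might also see a conflict with protocol 9.4.1, which mentions model-based imputation. That clause is permissive and leaves details to the SAP, so there is no conflict. Grouping in protocol 9.4.6 is likewise permissive, and SAP 6.3 does not forbid it.

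**Conclusion.** The point holds conditionally. SAP 6.3 prescribes outcome-dependent deletion if low death counts are what is suppressed, and it is hard to reconcile with a protocol that makes small counts available for analysis in three states and gives individual-level death data in the fourth. The effect is nil if all counts are released. With only Massachusetts masked at 1 to 10, relative rates shift little (about 0.77 to 0.81 against 0.80), while adjusted rates in sparse levels can fall to about 0.87 of full-data values. These sizes rest on assumed community sizes, level shares and threshold. The primary, research-site and rural/urban analyses use community totals and are unaffected. This is a cheap improvement, not a threat to the trial's main result.

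**What to change.** Replace the exclusion sentence in SAP 6.3 with: *Subgroup models for opioid overdose deaths use the unsuppressed counts released for analysis; suppression applies only to published tables.*

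For any cell that still cannot be released (for example in Massachusetts, if the model cannot be run on its individual-level death data):
- State the site, trigger field, threshold and handling of zeros.
- Report the records lost by wave and level, not only in total.
- Add a sensitivity analysis that treats the masked count as lying within its known range. With Massachusetts masked at 1 to 10, setting every masked cell to 1, or every one to 10, gives relative rates of 0.78 to 0.85. Opposite extremes by wave give 0.37 to 1.86 with four race/ethnicity levels, so worst-case bounds alone say little there.
- Combine levels, as protocol 9.4.6 permits, only where a level is not estimable. Keep the planned Black and Hispanic levels wherever they can be estimated.

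The cost is SAP wording and a small rerun, possibly inside the Massachusetts data environment. SAP 6.2.5 and 6.2.6 say results have already been disseminated, so any rerun should be labelled post hoc.
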